8.4 CSF PK Sampling Schedule

Subjects included in Cohorts 5 through 8 will have one CSF sample collected, via lumbar puncture, at one of the following timepoints: 24, 36, 168, or 336 hours post-start of infusion.

NS101 concentrations in CSF will be presented in the listings, as well as the ratio of NS101 in serum to NS101 in CSF at the applicable time-matched timepoint, i.e. serum NS101/CSF NS101 at time xx hrs.

8.5 Assessment of Dose Proportionality

An exploratory assessment of dose proportionality will be undertaken for the PK parameters AUC_{0-t}, AUC_{0-inf}, and C_{max}. The power model will be used and will include the PK parameter as the response variable and dose (mg) as the explanatory variable. For this model, the variable dose will be treated as a continuous variable. All cohorts will be considered for the analysis as a minimum of three doses are required. The form of the model is as follows:

This document is confidential.

PK Parameter = $e^\alpha \times \text{dose}^\beta \times e^\epsilon$, where dose ≥ 0 , and e^ϵ represents the associated error.

Thus, perfect dose proportionality is met when $\beta=1$ (ignoring error). This becomes a linear relationship following a natural-log transformation, to which a linear regression will be fit by ordinary least squares (OLS):

$\ln(\text{PK Parameter}) = \alpha + \beta \times \ln(\text{dose}) + \epsilon$ where dose > 0 , and ϵ represents the associated error.

The estimate of β , together with a 90% confidence interval (CI), will be provided (for each PK parameter model), and this will be used to quantify dose proportionality. According to Hummel et al. (2009), the following criterion may be used for exploratory dose proportionality evaluations: If the (two-sided) 90% CI for β is wholly contained within the interval, $[1+\ln(0.5)/\ln(\rho), 1+\ln(2)/\ln(\rho)]$, then dose proportionality is suggested across the investigated dose range. Here, ρ is defined as the ratio of the highest to lowest dose. This interval criterion will be reported along with the corresponding 90% CI estimate for β (presented to three decimal places).

The SAS code for the analysis model will follow the format given below (using the mixed procedure to fit the linear regression). The input variables (or datasets) are depicted in italicized red text and have been given generic names.

```
proc mixed data=dataset order=data;
  model ln_pk_parameter = ln_dose / solution;
  estimate 'Beta Estimate' ln_dose 1 / cl alpha=0.1;
  ods output estimates = estimates;
run;
```

The PK parameter values estimated from the power model will be plotted against dose. This plot will also include individual subject values with the observed mean \pm SD (PK parameter versus dose level).

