	After database lock, the power model approach will also be performed on AUC_{0-24} , AUC_{0-in} , AUC_{0-inf} , and C_{max} data to assess the dose-proportionality when all dose levels will be completed. Non-parametric analysis will also be performed on the untransformed T_{max} data.

Immunogenicity:
Incidence and titer of ADAs and NAbs will be assessed.

4. Schedule of Events

	Screening				Co	ohorts 1 to	81				Study Exit
PROCEDURE	D-28 to D-2	D-1	D1	D2	D3	D5±1	D8±1	D15±1	D22±2	D29±2	(Day 60 ± 3) or E.T.
Informed Consent	X										
Demographic Data	X										
Medical and Medication Histories	X										
Review and Monitoring of AEs and Concomitant Medications	X	X	X	X	X	X	X	X	X	X	X
Physical Examination ²	X	X			X		X	X			X
Body Measurements ³	X	X									
Vital Signs (BP, HR, RR, OT) ⁴	X	X	X	X^{13}	X	X	X^{13}	X^{13}	X	X	X
ECG	X		X^5	X^5	X ⁵	X	X	X	X	X	X
S-STS	X										X
Hematology	X	X^6			X		X	X		X	X
Biochemistry	X	X^6			X		X	X		X	X
Coagulation	X	X^6			X		X	X		X	X
Serology (HIV and Hepatitis B and C)	X										
Urinalysis	X	X^6			X		X	X		X	X
Urine Drug Screen	X	X									
Alcohol Breath Test	X	X									
Confinement		X	X	X	X						
Randomization			X^7								
Injection Site Evaluation			X^8	X^8	X^8	X^8	X^8				
Study Treatment Administration			X^9								
Blood PK Samples ¹⁰			X	X	X	X	X	X	X	X	X
Blood PD Samples ¹¹			X	X	X	X	X	X	X	X	X
Lumbar Puncture for CSF Samples ¹²				X			X	X			
Pulse oximetry (PO) ¹⁴				X			X	X			
Blood Samples for ADA Assessment ¹⁵			X			X		X	X	X	X

- 1 Dose escalation will not occur until safety and tolerability up to Day 8±1 and available PK data up to 48 hours post-start of infusion for at least 7 subjects are assessed in the preceding cohort, and the study drug is deemed safe by the SRC.
- 2 A complete physical examination will be performed at screening and study exit. A brief physical examination will be performed on Day -1, Day 3 (approximately 48 hours post-start of infusion), Day 8±1, and Day 15±1, and as symptoms directed.
- 3 Height, weight, and BMI will be collected at screening. Body weight will be collected on Day -1 to calculate the dose to be administered per subject.
- 4 BP, HR, RR, and OT: screening, Day -1, and study exit. BP, HR, and OT: Day 1 pre-start of infusion and 1.5, 2, 4, 6, 8, 12, 24 (Day 2), and 48 (Day 3) hours post-start of infusion, as well as on Days 5 ±1, 8±1, 15±1, 22±2, and 29±2.
- 5 ECG: Day 1 pre-infusion and 1.5, 4, 8, 12, 24 (Day 2), and 48 (Day 3) hours post-start of infusion.

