9.2.3.1 Events Within One Dose Level

Dose escalation will be halted if any of the events described below occur within one dose level:

- Individual stopping rules met for ≥ 2 subjects in the same cohort suggesting that subjects receiving higher dose levels would be at risk for similar adverse drug reactions.
- The occurrence of one SAE considered at least possibly related to the study drug.
- The occurrence of CTCAE grade 3 considered at least possibly related to the study drug in ≥ 2 subjects and independent of within or not within the same system organ class (SOC).
- Clinically significant abnormalities of the same character, at least of CTCAE grade 2, and considered at least possibly related to the study drug in ≥ 2 subjects, with regards to:

- o the physical examination;
- o ECG;
- o vital signs; or
- o clinical laboratory parameters.
- Mean exposure (AUC₀₋₂₄) exceeding 132 000 000 **ng.h/mL or concentrations** reaching 8 830 000 ng/mL.

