13.6 Statistical Analyses

Individual and mean serum or plasma concentration versus time curves will be presented for both linear and semi-log scales for NS101 and FAM19A5. Descriptive statistics (arithmetic and

geometric means, SD, CV%, Min, Max, and median) of the serum or plasma concentrations versus time will be presented as well for the PK and PD parameters.

Interim PK analyses will be performed for each cohort. Summary statistics will be used to describe the PK profile for this cohort. Dose proportionality may be assessed within different dose ranges if deemed appropriate with at least three doses using the power model approach. Dose-response relationship may be performed using Logistic Regression plots to assess the relationship between PK data after single dose administrations and specific AEs, when data permitting.

Summary statistics will be used to describe the PK profile for each cohort. After data base lock, the power model approach will be performed on the ln-transformed PK parameters AUC_{0-24} , AUC_{0-inf} , AUC_{0-inf} , and C_{max} , and data to investigate dose-proportionality. Non-parametric analysis will also be performed on the untransformed T_{max} data.

14. Regulatory Considerations and Quality Assurance

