11.11 COVID-19 Visit Impact

COVID-19 Visit Impact data will be listed.

This document is confidential.

12. Changes from Analysis Planned in Protocol

None.

This document is confidential.

13. Reference List

This document is confidential.

14. Programming Considerations

- All TLFs, and statistical analyses will be generated using SAS for Windows, Release 9.4.
- Phoenix® WinNonlin® version 8.3.4 (Certara USA, Inc., Princeton, NJ) will be used for all PK analyses. This software was validated by Syneos in compliance with US 21 CFR Part 11 regulation.

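### The SAP leaves AUC0-24 out of the post-lock dose-proportionality model that the protocol specifies, yet declares no changes from the protocol (low severity)

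*SAP*

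**What the plan says.** The protocol describes the final dose-proportionality analysis twice. The synopsis (Statistical Analyses) says that "the power model approach will also be performed on AUC_{0-24} , AUC_{0-in} , AUC_{0-inf} , and C_{max} data" once all dose levels are complete. Section 13.6 says that "the power model approach will be performed on the ln-transformed PK parameters", again naming AUC0-24 first, and times this after database lock. Both statements are firm. Only the interim proportionality assessment during escalation is optional.

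The second AUC in each protocol list is garbled or repeated: the synopsis prints AUC0-in, and section 13.6 prints AUC0-inf twice. AUC0-t was probably meant. AUC0-24 is clear in both places.

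SAP 8.5 opens with "An exploratory assessment of dose proportionality will be undertaken for the PK parameters" and then names AUC0-t, AUC0-inf and Cmax. AUC0-24 is absent. SAP section 12, "Changes from Analysis Planned in Protocol", contains the single word None.

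AUC0-24 appears elsewhere in both documents. It is one of the serum PK parameters under the secondary endpoints (protocol section 7, SAP section 4). SAP 8.3 derives it and summarises it by dose level. Protocol 9.2.3.1 halts escalation on "Mean exposure (AUC₀₋₂₄) exceeding 132 000 000" ng.h/mL, or on concentrations reaching 8 830 000 ng/mL.

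**The concern.** An analysis that the protocol commits to would not be run if the programmers followed the SAP, and the section meant to disclose such departures says there are none. A reader of the study report who relied on SAP section 12 would not know that a planned result was missing.

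The dropped parameter is also the only AUC in the protocol's exposure limit. A final estimate of how first-day exposure scales with dose, with its interval, would be a natural companion to that limit when later studies are designed. What is at stake is that estimate and the accuracy of the SAP's declaration.

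**Working it through.** **1. Parameter lists side by side**

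| Source | AUC0-24 | Second AUC | AUC0-inf | Cmax |
|---|---|---|---|---|
| Protocol synopsis | yes | printed AUC0-in | yes | yes |
| Protocol 13.6 | yes | AUC0-inf repeated | yes | yes |
| SAP 8.5 | **no** | AUC0-t | yes | yes |

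Reading the second AUC as AUC0-t, the protocol list minus the SAP list is AUC0-24 alone.

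**2. What the omitted fit would have reported**

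SAP 8.5 asks for the slope β, a two-sided 90% CI, and a check that the CI lies within 1 ± ln(2)/ln(ρ), where ρ is the ratio of highest to lowest dose. On the mg/kg scale ρ = 48/0.25 = 192, so ln(2)/ln(192) = 0.693/5.257 = 0.132 and the interval is 0.868 to 1.132. SAP 8.5 models dose in mg, so the actual ρ will depend on body weights that the documents do not give.

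**3. How much of total exposure falls in the first 24 hours**

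Under a mono-exponential decline the share of AUC0-inf is 1 − exp(−ln2 × 24/t½). The protocol's animal half-lives give:
- 53.7 h (rat, Table 1): 27%
- 78.0 h (rat, Table 6, Week 1): 19%
- 181.0 h (rat, section 5.2.4.2): 9%
- 329.9 h (mouse, Table 5): 5%

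The range is about 5% to 27%. Two Table 1 entries read 613 h, apparently with a lost decimal point, and are not used. The approximation is rough, because section 5.2.4.3 describes a biphasic decline.

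Table 7 needs no such assumption. On Day 1 in rats, in millions of ng.h/mL, AUC0-24 over AUC0-168 is:
- 50 mg/kg: 19.2/49.8 = 39% (males), 17.5/46.6 = 38% (females)
- 150 mg/kg: 62.5/168 = 37%, 61.6/191 = 32%
- 300 mg/kg: 132/383 = 34%, 120/393 = 31%

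Even within one week, then, 61% to 69% of exposure came after the first day.

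**4. Whether the retained parameters stand in for AUC0-24**

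Using the same Day 1 means, the end-to-end slope from 50 to 300 mg/kg is ln(ratio of exposures)/ln(6):

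| Parameter | Males | Females |
|---|---|---|
| AUC0-24 | ln(132/19.2)/ln 6 = 1.08 | ln(120/17.5)/ln 6 = 1.07 |
| AUC0-168 | ln(383/49.8)/ln 6 = 1.14 | ln(393/46.6)/ln 6 = 1.19 |
| Cmax | ln(8.83/1.39)/ln 6 = 1.03 | ln(8.90/1.24)/ln 6 = 1.10 |

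The longer AUC differs from AUC0-24 by 0.06 in males and 0.12 in females, which is not small against a half-width of 0.132. Cmax is closer, within about 0.04 in males and 0.03 in females. AUC0-24/Cmax stays between 13.4 h (61.6/4.60) and 14.9 h (132/8.83) over the six groups. These are animal means over a six-fold range. They show that slopes can differ by parameter and do not predict the human result.

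**The case against.** The best defence is that little is lost. The analysis is labelled exploratory, and dose proportionality is neither an objective nor an endpoint in its own right. AUC0-24 is still derived, listed and summarised with geometric means by dose level, so a reader can see how it scales. Cmax, also a first-day measure after a 60-minute infusion, stays in the model and tracked AUC0-24 closely in the rat data. All of that stands, and it keeps the severity low. It does not supply the planned slope and interval, and it does not make section 12 accurate.

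Three stronger readings are tempting, and the documents do not support them.

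- A reader might infer that the omission weakens the escalation limit. The rule compares a cohort's observed mean AUC0-24 with a fixed ceiling during escalation and uses no slope. The omitted model runs after database lock. The rule also has a concentration limb.
- A reader might infer that nothing left in the SAP bears on first-day proportionality. The descriptive summaries and the Cmax model both do.
- A reader might take only the longer half-lives (181 to 330 h) and conclude that AUC0-24 is just 5% to 9% of total exposure. The protocol reports much shorter half-lives as well, and Table 7 shows a larger early share.

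**Conclusion.** The discrepancy is real. The SAP omits AUC0-24 from an analysis that the protocol specifies in two places, and its statement that nothing changed is inaccurate. The consequence is limited to one slope, its 90% CI and its criterion check, for a parameter that is part of a secondary endpoint and is the AUC in the exposure limit. The slopes for AUC0-t and AUC0-inf cannot be assumed equal to it; the Cmax slope is a closer but not identical guide. No sample size, error rate or dosing decision is affected.

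The count of one dropped parameter assumes that the garbled second AUC in the protocol means AUC0-t. If it does not, AUC0-t is a further unrecorded difference. The AUC0-24 finding does not depend on that. Severity is low, because the analysis is exploratory.

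**What to change.** Add AUC0-24 to the parameter list in SAP 8.5, with the same power model, 90% CI and acceptance interval as the other parameters. If the omission is deliberate, replace None in SAP section 12 with a statement that AUC0-24 was removed from the power model, and give the reason. It would help to confirm there, in the same edit, that the protocol's second AUC is AUC0-t.

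The cost is one more run of existing code, so three fits become four, on a parameter that SAP 8.3 already derives. No new data are needed, and the model and criterion do not change.

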8.6 Non-parametric Assessment of T_{max}

A non-parametric assessment to test for central location differences among dose levels, will be undertaken for T_{max}. All cohorts will be considered for the analysis as a minimum of two dose levels are required.

An overall Kruskal-Wallis Test for differences in PK values across dose levels will be conducted (e.g., H₀: on average, T_{max} values are equal across dose levels, and H_a: on average, PK parameter values differ among at least two distinct dose levels). If the P-value is significant at the 5% level, then PK parameter values are considered unequal across all dose levels. If the P-value is not significant, then PK similarity may be suggested across the investigated dose range.

The SAS code to perform the test will follow the format given below (using the Npar1way procedure). The input variables, datasets and labels are depicted in italicized red text and have been given generic names.

```
proc npar1way data=dataset wilcoxon;
  class treatment;
  var pk_parameter;
  ods output KruskalWallisTest = Ktest;
run;
```

9. Pharmacodynamic Analyses

This document is confidential.

All plasma PD summaries and analysis will be conducted on the PD population.

Plasma PD will be evaluated through the variation of the normalized and actual level of FAM19A5 following administration of NS101. Normalized and actual FAM19A5 level, absolute changes and percent changes from normalized and actual baseline in FAM19A5 level will be summarized for the PD population by dose level, and timepoint, using descriptive statistics.

Absolute changes from normalized and actual baseline FAM19A5 levels (Δ FAM19A5) will be determined. Baseline is defined as the Day 1 pre-dose plasma PD sample. At each post-dose measurement of FAM19A5, the Day 1 pre-dose plasma PD sample will be subtracted to calculate Δ FAM19A5. For percent change from normalized and actual baseline Δ FAM19A5 will be divided by Day 1 pre-dose plasma PD sample and multiplied by 100.

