3.3 Treatment Assignment

All subjects enrolled will receive a single infusion of NS101, or matching placebo, under fasting conditions over a period of approximately 1 hour, at the target dose levels listed in the table below. Each subject's body weight on Day -1 will be used to calculate the dose required, based on their assigned dose level [body weight (kg) x dose level (mg) = administered dose (mg)].

Cohort Number	Dose level	Number of subjects receiving NS101	Number of subjects receiving placebo
1	0.25 mg/kg	6 (1 sentinel, 5 non-sentinel)	2 (1 sentinel, 1 non-sentinel)
2	0.75 mg/kg	6 (1 sentinel, 5 non-sentinel)	2 (1 sentinel, 1 non-sentinel)
3	1.50 mg/kg	6 (1 sentinel, 5 non-sentinel)	2 (1 sentinel, 1 non-sentinel)
4	3.0 mg/kg	6 (1 sentinel, 5 non-sentinel)	2 (1 sentinel, 1 non-sentinel)
5	6.0 mg/kg	6 (1 sentinel, 5 non-sentinel)	2 (1 sentinel, 1 non-sentinel)
6	12.0 mg/kg	6 (1 sentinel, 5 non-sentinel)	2 (1 sentinel, 1 non-sentinel)
7	24.0 mg/kg	6 (1 sentinel, 5 non-sentinel)	2 (1 sentinel, 1 non-sentinel)
8	48.0 mg/kg	6 (1 sentinel, 5 non-sentinel)	2 (1 sentinel, 1 non-sentinel)

Note: Adjustments to the currently outlined dose levels may be made based on data from completed dose levels. However, the dose to be administered in a given cohort will not exceed the one currently outlined in the protocol.

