8.2 Serum PK Sampling Schedule

A total of 21 blood samples will be collected in each cohort for serum PK analysis: pre-start of infusion and 0.25, 0.5, 0.75, 1, 1.25, 1.5, 2, 4, 6, 8, 12, 24, 36, 48, 96, 168, 336, 504, 672, and 1416 hours post-start of infusion.

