8.3 Serum PK Parameters

Serum PK parameters will be presented in data listings and summarized in tables by dose level, using descriptive statistics (n, arithmetic mean, SD, CV%, geometric mean, min, median, and max).

The serum concentrations of NS101 will be used to calculate the following parameters by standard non-compartmental methods:

Parameter	Definition
AUC _{0-inf}	area under the concentration-time curve from time zero to infinity (extrapolated), calculated as $AUC_{0-t} + C_t/\lambda_z$, where: C_t = the last measurable concentration

This document is confidential.

Parameter	Definition
AUC _{0-t}	area under the concentration-time curve from time zero until the last observed concentration
AUC ₀₋₂₄	area under the concentration-time curve from time zero to time 24 hours
Cl	apparent body clearance, calculated as dose / AUC _{0-inf}
C _{max}	maximum observed concentration
K _{el}	elimination rate constant
T _{½ el}	terminal elimination half-life, calculated as ln 2 / K _{el}
T _{max}	time when the maximum concentration is observed
Residual area	percentage of the area extrapolated for calculation of area under the concentration-time curve from time zero to infinity, calculated as [(AUC _{0-inf} - AUC _{0-t}) / AUC _{0-inf}] * 100
V _z	apparent volume of distribution, calculated as dose / (K _{el} * AUC _{0-inf})

AUC_{0-t}, AUC₀₋₂₄, and AUC_{0-inf} will be calculated using the linear trapezoidal method (linear up log down).

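### SAP 8.6 reads a non-significant Kruskal-Wallis test on Tmax as suggesting PK similarity and a significant one as all dose levels unequal; neither follows from the test

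*SAP*

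**What the plan says.** SAP 8.6 plans one overall Kruskal-Wallis test of Tmax across all dose levels. The null is that Tmax is on average equal across doses. The alternative is that "PK parameter values differ among at least two distinct dose levels". Two reading rules follow:

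- significant at 5%: "then PK parameter values are considered unequal across all dose levels";
- not significant: "If the P-value is not significant, then PK similarity may be suggested across the investigated dose range".

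The section gives no similarity margin, confidence interval, effect estimate or pairwise follow-up. Protocol 13.6 asks only for a non-parametric analysis of untransformed Tmax, so the reading rules are the SAP's own.

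SAP 8.5, just before, handles a similar question differently. It suggests dose proportionality only if the 90% CI for the power-model slope "is wholly contained within the interval" that the section specifies.

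For description, SAP 8.3 states: "Serum PK parameters will be presented in data listings and summarized in tables by dose level". Tmax is among those parameters.

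**The concern.** There are three faults, all in the reading rules and not in the choice of test.

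1. A null result may be reported as similarity. With no margin and no interval, non-rejection can mean that the doses are alike or only that the data are few. Six active subjects per dose (SAP 3.3), with a sample size not based on a power calculation (SAP 3.2), make the second explanation a live one.
2. A significant result is to be reported as inequality across all dose levels. That is stronger than the alternative stated one sentence earlier.
3. Both rules refer to PK or PK parameters, although only Tmax is tested. A null Tmax result could be written up as similar PK over the whole range, 48 / 0.25 = 192-fold.

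The study is meant to inform doses and regimens for later trials, and a reading rule written in advance tends to pass straight into the report.

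**Working it through.** **Inputs.** From the SAP: 8 dose levels (3.3), 6 active subjects each, so N = 48; one overall test at 5% (8.6); nominal sampling times "0.25, 0.5, 0.75, 1, 1.25, 1.5, 2, 4, 6, 8, 12, 24, 36, 48" h and later (8.2). Neither document gives a Tmax SD, a relevant difference or a power figure, so there is no stated figure to reproduce and the shifts below are assumptions.

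**Non-significant branch.** The statistic is H = 12 / [N(N + 1)] × Σ(Rj² / n) − 3(N + 1), with Rj the rank sum at dose j and n = 6, referred to chi-square on 8 − 1 = 7 df. With normal data and 20,000 simulated trials per scenario, the rejection rates are:

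| True pattern | 1 SD | 1.5 SD | 2 SD |
|---|---|---|---|
| Top dose only shifted | 19.6% | 45.1% | 73.3% |
| Linear trend, lowest to highest dose | 22.2% | 53.2% | 83.0% |
| Top two doses shifted | 40.0% | 81.5% | 98.1% |
| Top four doses shifted | 55.6% | 93.9% | 99.9% |

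With no true difference the rejection rate is 3.8%. A second, separate set of 20,000 trials per scenario gave 19.3%, 44.9% and 72.9% for the first row and 22.3%, 52.5% and 82.8% for the second, which agrees within simulation error.

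The share of trials in which the SAP rule would allow a similarity statement is 1 minus power. For the first two patterns:

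- 1 SD: 80% and 78%;
- 1.5 SD: 55% and 47%;
- 2 SD: 27% and 17%.

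**Sampling grid.** Tmax was also simulated as log-normal (assumed median 1.25 or 2 h, log-SD 0.3 or 0.6), moved to the nominal sampling times, with the tie-corrected statistic and 8,000 trials per scenario. Power for the same two patterns was 16–21%, 38–51% and 66–82%, slightly lower than above.

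**Significant branch.** Eight doses make 8 × 7 / 2 = 28 pairs. If only the top dose differs, 7 × 6 / 2 = 21 of them are equal. At 2 SD the test still rejects in 73% of trials, and with one dose fully separated from seven identical ones it rejected in every run. Rejection therefore cannot show that all levels are unequal.

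**Comparison with SAP 8.5.** Its interval for a nominal dose ratio of 192 runs from 1 + ln(0.5)/ln(192) = 0.868 to 1 + ln(2)/ln(192) = 1.132. A wide CI fails that criterion. Under 8.6 the same imprecision makes a similarity statement more likely.

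**What an interval could show.** For two doses at 6 v 6, the t approximation gives a 90% half-width of t(0.95, 10 df) × √(2/6) = 1.05 SD. Simulated Hodges-Lehmann limits average 1.08 SD. Only a margin wider than about 1.1 SD could support similarity between two doses.

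**Separate check on AUC0-24.** The protocol synopsis and Protocol 13.6 list AUC0-24 for the power model after database lock. SAP 8.5 begins "An exploratory assessment of dose proportionality will be undertaken for the PK parameters" and names only AUC0-t, AUC0-inf and Cmax. SAP Section 12 declares no changes from the protocol.

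**The case against.** The case against giving this weight has several parts.

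- *The stakes are low.* Tmax is one secondary PK parameter, the similarity wording is hedged, and dose escalation rests on adverse events, mean AUC0-24 and concentrations (Protocol 9.2.3). This stands and caps the importance of the point.
- *A charitable reading exists.* The section's title, opening sentence and null hypothesis all name Tmax, so PK similarity may mean similarity of Tmax. Likewise, unequal across all levels may be loose wording for not all equal. Both are possible. As written, though, the second rule exceeds its own alternative, and no reading turns a null result into evidence of similarity.
- *The effect sizes are assumed and in SD units.* This also stands. Under the grid assumptions a 1 SD upward shift is 1.25 × (e^0.3 − 1) = 0.4 h at the least and 2 × (e^0.6 − 1) = 1.6 h at the most. That is small beside the 329.9 h half-life the protocol cites from mice as potentially expected in humans, and nothing in the documents says that such a shift matters.
- *The Tmax model is crude.* With median 1.25 h and log-SD 0.6, about 20% of simulated values fall before 0.75 h, inside a constant-rate infusion of about 60 minutes. Also, SAP 8.1 uses actual times, so ties would be fewer than on the nominal grid. These are fair criticisms of the grid version, but the version without ties gives nearly the same power, and the logical fault needs no simulation.
- *AUC0-24 is a different issue.* Agreed. It is reported here as a separate, smaller point.

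**Conclusion.** The concern holds. Both reading rules in SAP 8.6 permit conclusions that the test cannot support, and a third fault is that they are worded for PK in general when only Tmax is tested. This does not depend on any assumed effect size.

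How often the first rule would mislead does depend on assumptions. For a 1 SD difference confined to the top dose, or spread as a trend, similarity could be suggested in 78–80% of trials. At 2 SD the figure is 17–27%. Shifts affecting several doses are found more often: 40% power for the top two doses and 56% for the top four at 1 SD.

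The consequence is limited to what the report may say about Tmax. The descriptive tables remain, and no escalation rule or primary endpoint uses the test. It should be corrected because correction is nearly free.

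For AUC0-24, only the power-model slope is lost. The parameter is still calculated and summarised, and the escalation rule compares its mean with a fixed threshold. The omission is nevertheless an undeclared departure from the protocol.

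**What to change.** Keep the Kruskal-Wallis test. In SAP 8.6, replace the two reading rules with wording such as:

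> A P-value below 0.05 will be taken to show that Tmax differs between at least two dose levels. Otherwise the report will state that no difference in Tmax between dose levels was detected; this is not evidence of similarity.

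Write Tmax wherever 8.6 now refers to PK values, PK parameter values or PK similarity.

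Optionally, and as description only, report Hodges-Lehmann differences in Tmax from the lowest dose with 90% CIs, noting the expected half-width of about 1.1 SD.

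Separately, either add AUC0-24 to the SAP 8.5 power model or record its removal in Section 12.

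The cost is two replaced sentences and a change of terms in 8.6, plus one line in 8.5 or Section 12. No new data and no new test are needed.
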